Each concomitant drug must be individually assessed against all exclusion criteria/prohibited medications and local prescribing information of azacitidine (Vidaza® (Azacitidine) USPI (2008)) and venetoclax (Venclexta® (Venetoclax) USPI (2020)). If in doubt, the investigator should contact the Novartis medical monitor before a participant starts treatment or allowing a new medication to be started. If the participant has already started treatment, contact Novartis medical monitor to determine if the participant should continue study treatment. Supportive therapy including prophylactic antibiotic and antifungal treatments, transfusions, growth factors (e.g. GCSF, ESA) etc. will be administered at the discretion of the investigators according to their local standard of care.

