If a narrow therapeutic index P-gp or BCRP substrate must be used, it should be used with caution. For an orally administered P-gp or BCRP substrate sensitive to inhibition in the gastrointestinal tract (e.g., dabigatran etexilate), its administration should be separated from venetoclax administration as much as possible to minimize a potential interaction.

Anticoagulation therapy is permitted if the participants are already at stable dose of warfarin or stable doses of low molecular weight heparin (LMWH) for > 2 weeks at time of first dose and International Normalized Ratio (INR) should be monitored closely. Participants who develop a new requirement for anticoagulant therapy during the conduct of the study may remain on study after documented discussion with the Novartis medical monitor. However, ongoing anticoagulant therapy should be temporarily discontinued to allow bone marrow sampling according to the institutional guidelines.

Anti-hypertensive therapy is allowed as concomitant medications; however because transient hypotension has occurred during infusions of monoclonal antibodies, consideration should be given to withholding anti-hypertensive medications for 12 hours prior to infusion with sabatolimab.

6.2.2 **Prohibited medication**

During the course of the study, participants must not receive additional investigational drugs, devices, chemotherapy, or any other therapies that may be active against cancer or modulate the immune response.

The use of systemic steroid therapy at immunosuppressive dose (> 10 mg/day of prednisone or equivalent) and other immunosuppressive drugs are not allowed except for the treatment of infusion reaction, immune related adverse events (irAEs), for prophylaxis against imaging contrast dye allergy or in the context of transfusion, for replacement-dose steroids in the setting of adrenal insufficiency or for treatment of transient exacerbation of other underlying diseases such as chronic obstructive pulmonary disease requiring treatment for \leq 3 weeks.

Systemic corticosteroids required for control of infusion reactions or irAEs must be tapered and be at non-immunosuppressive doses ($\leq 10 \text{ mg/day}$ of prednisone or equivalent) before the next sabatolimab administration.

If more than 10 mg/day prednisone is used, sabatolimab should be temporarily interrupted until the participant receives 10 mg/day or less of prednisone.

Topical, inhaled, nasal and ophthalmic steroids are allowed.

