8.3 Efficacy

8.3.1 Efficacy assessments

Disease response will be assessed locally by the investigator in all participants (MDS) according to modified IWG for MDS and WHO criteria (Cheson et al 2000, Cheson et al 2006, Arber et al, 2016, Platzbecker 2019). Response criteria are described in Table 8-2.

Investigators will assess and document response/progression at each time point as per the visit schedule. For efficacy analyses, baseline assessment is defined as the last non-missing assessment on or before the date of sabatolimab.

In addition, the hematological improvement per modified IWG-MDS criteria (Cheson et al 2006) will be assessed in all enrolled participants to report specific hematologic improvement (HI) of cytopenias in the three hematopoietic lineages: erythroid (HI-E), platelet (HI-P), and neutrophil (HI-N).

Response category	Definition [#]
Complete remission (CR)	Bone marrow:
	<= 5% blasts with normal maturation of all cell lineages. (Note: Persistence of dysplasia will be noted but does not preclude achievement of complete remission [CR])
	Peripheral blood:
	1. Hgb $\geq 10 \text{ g/dl}$ AND
	2. Platelets $\geq 100*10^9$ /L AND
	3. Neutrophils $\geq 1.0*10^9$ /L AND
	4. Blasts 0%
	(Note: the participant must not receive RBC or platelet transfusions, myeloid growth factor within 2 weeks before this disease assessment)
marrow Complete remission (mCR)	Bone marrow:

Table 8-2Modified response classification per IWG-MDS criteria (Platzbecker et
al 2019, Cheson et al 2006, Cheson et al 2000)

Response category	Definition [#]
	<= 5% blasts and blast count decrease by \geq 50% compared to baseline
	Peripheral blood/transfusion: Marrow CR may be achieved with or without improved blood counts or with or without transfusions
Partial remission (PR)	All CR criteria except
	Bone marrow: $\geq 50\%$ decrease from baseline in blasts in bone marrow AND blast count in bone marrow $> 5\%$
Stable Disease (SD)	Failure to achieve at least PR, but no evidence of progression for >8 weeks
Relapse from CR	Only in participants with a CR
	At least 1 of the following criteria is met: [in absence of another explanation not due to MDS, such as acute infection, bleeding, hemolysis, etc. Note that observation of peripheral blasts is not a sufficient criterion for relapse. However in that case, a bone marrow examination should be made to determine whether relapse has occurred]
	1. Return to baseline bone marrow blast percentage

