12.4.1.2 Cohort 2 of Safety run-in (Part 1) and Expansion (Part 2)

The primary clinical question of interest is the following:

Is Sabatolimab 800 mg Q4W in combination with fixed doses of azacitidine (75 mg/m² Day 1-7) and venetoclax (400 mg Day 1-14) associated with improved efficacy (i.e. CR rate $\geq = 50\%$) for participants with high or very high risk MDS?

The primary endpoint (combining data from cohort 2 of the Safety run-in (Part 1) and the Expansion (Part 2) (i.e. sabatolimab 800 mg (Q4W)) is the proportion of participants achieving a complete remission (CR) as per investigator assessment (Section 2 and Table 2-1).

The primary efficacy estimand is described by the following five attributes:

- **Population:** Adult participants not eligible for intensive chemotherapy nor for HSCT with high or very high risk MDS (IPSS-R criteria (Greenberg et al 2012)) as assessed locally by the investigator.
- Variable: Best overall response among all disease response assessments as assessed by investigator per modified IWG MDS criteria (Cheson et al 2006) up to new anti-cancer therapy (including HSCT).
- **Treatment:** Study treatment is sabatolimab 800 mg Q4W + azacitidine (75 mg/m² Day 1-7) + venetoclax (400 mg Day 1-14). Participants will continue treatment until a reason of treatment discontinuation is met (e.g. progression, unacceptable toxicity, HSCT) (Section 6.1.5).
- Intercurrent events:
 - **Study treatment modification:** all CR will be taken into account regardless of any study treatment component interruption, dose adjustment or permanent discontinuation (Section 6.1.5).
 - **Concomitant medications and supportive care:** A participant may receive blood transfusion as supportive care and prophylactic treatment as clinically indicated (e.g. antiemetics, antibiotics, antifungals, Section 6.2.1). All CR will be taken into account

regardless of any concomitant medication administration including prohibited medications.

- New anti-cancer therapy/HSCT: CR achieved after initiation of a new anti-cancer therapy or HSCT will not be taken into account.
- Summary measures: The CR rate and the 95% confidence interval (CI).

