12.4.2.2 Cohort 2 of Safety run-in (Part 1) and Expansion (Part 2)

CR primary analysis

The CR primary analysis will be performed for participants from cohort 2 of Safety run-in (Part 1) and Expansion (Part 2) treated with sabatolimab 800 mg Q4W.

A Bayesian design will be used in order to estimate the CR rate in the FAS (Full Analysis Set) and to provide inferential summaries (e.g., mean, median, standard deviation, 95% credible intervals, and interval probabilities) based on Bayesian posterior distribution of the CR rate. Assuming a non-informative prior distribution (Beta(1,1)), the distribution of the CR rate will be updated with all available data from the participants included in the FAS.

The decision criteria for trial success are the following:

- Posterior median of CR rate is \geq 50% and
- Posterior probability that CR rate is > 39% is at least 97.5%.

The cumulative posterior distribution will be used to derive the probability that the true CR rate is superior to 50%. Based on preliminary efficacy data observed with the combination azacitidine + venetoclax (Wei et al 2019), a 50% CR rate is a reasonable threshold to be considered in this specific setting.

The results will be also presented with a frequentist formulation. The CR rate and the exact 95% confidence interval (CI) (Clopper CJ and Pearson ES 1934), as well as the 1-sided p-value will be provided on the FAS. The test will be performed using an overall one-sided 2.5% level of significance. Thus, the null hypothesis (H₀:CR \leq 39%) will be rejected if the lower bound of the two-sided 95% exact CI is >39%.

The analysis will be performed using data up to the analysis data cut-off date, which will be 6 cycles after the last participant is enrolled.

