2.5.1.2 Cohort 2 of Safety run-in (Part 1) and Expansion (Part 2)

The primary endpoint is the proportion of participants included in the FAS and assigned to sabatolimab at the 800 mg Q4W dose level (in both safety run-in and expansion parts) who achieved a complete remission (CR) as per investigator assessment.

Response assessment rules

Response assessment will be performed by the investigator according to the assessment schedule depicted in protocol Table 8-1 based on available bone marrow assessment (C3D1, C7D1, C10D1, C13D1 and then C19D1, C25D1 and then every 12 cycles), hematology data (at D1, D8, D22 of the first 2 cycles and then D1 and D8 of each cycle until end of treatment and then every 12 weeks) and all transfusions records as detailed in s using the modified version of the published response criteria IWG for MDS. Moreover, response assessments can be performed at any time if clinically indicated, e.g. for confirmation of response but also for any suspicion of progression/relapse. These assessments are recorded as an unscheduled visit in the eCRFs and will be considered for the overall determination of response and progression/relapse with the respective assessment date.

The investigator does not determine best overall response, he/she is assessing only the response based on the given bone marrow and peripheral blood data, the history of transfusions and myeloid growth factor received within the last 2 weeks.

The best overall response (BOR) will be derived based on the CR primary endpoint rules by Novartis as below:

- CR = at least one determination of CR without progression or relapse from CR within the four weeks after CR
- mCR = at least one determination of mCR (and not qualifying for a CR).
- PR = at least one determination of PR (and not qualifying for a CR, mCR).
- HI = at least one determination of HI (and not qualifying for a CR, mCR, PR)
- SD = at least one SD assessment and not qualifying for CR, mCR, PR or HI).
- PD = progression after start of treatment and not qualifying for CR, mCR, PR, HI or SD.
- UNK = all other cases (i.e., not qualifying for confirmed CR or mCR or PR or HI and without SD or progression).

Details for the definition of response categories (captured in the eCRF by the Investigator) as defined in Table 8-2 of the protocol, are described in Table 2-2 below.

Response category	Definition [#]	
Complete remission (CR)	Bone marrow:	

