 - **Study treatment modification:** all CR will be taken into account regardless of any study treatment component interruption, dose adjustment or permanent discontinuation.
 - **Concomitant medications and supportive care:** A participant may receive blood transfusion as supportive care and prophylactic treatment as clinically indicated (e.g. antiemetics, antibiotics, antifungals). All CR will be taken into account regardless of any concomitant medication administration including prohibited medications.
 - New anti-cancer therapy/HSCT: CR achieved after initiation of a new anti-cancer therapy or HSCT will not be taken into account.
- Summary measures: The CR rate and the 95% confidence interval (CI).

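### The CR definition does not exclude ESA-supported hemoglobin, although ESA is allowed at the investigator's discretion, so the CR rate can be raised by support

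*Protocol*

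**What the plan says.** Protocol section 6.2.1 treats growth factors as supportive care and names ESA separately from G-CSF: "growth factors (e.g. GCSF, ESA) etc. will be administered at the discretion of the investigators according to their local standard of care". It sets no timing limit relative to response assessments. Section 6.2.2 prohibits "any other therapies that may be active against cancer or modulate the immune response" and does not name ESA.

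CR in protocol Table 8-2 (section 8.3.1) needs marrow blasts of at most 5%, hemoglobin of at least 10 g/dL, platelets of at least 100 × 10⁹/L, neutrophils of at least 1.0 × 10⁹/L and no peripheral blasts. A note adds that "the participant must not receive RBC or platelet transfusions, myeloid growth factor within 2 weeks before this disease assessment". SAP Table 2-2 repeats it. PR uses the same blood-count criteria. The short CR definition in protocol Table 2-1 has no support condition.

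SAP section 2.5.1.2 says that the investigator judges response from marrow and blood data and "the history of transfusions and myeloid growth factor received within the last 2 weeks". ESA is not in that list.

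Under concomitant medications and supportive care, the primary estimand counts every CR "regardless of any concomitant medication administration including prohibited medications" (protocol 12.4.1.2). SAP 2.5.1.2 says the same. CR is disregarded only after new anti-cancer therapy or HSCT.

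**The concern.** The note appears intended to stop supported counts from passing as remission: transfusion for hemoglobin and platelets, myeloid growth factor for neutrophils. Drug support for hemoglobin is the form left out. The term myeloid growth factor is not defined. Because section 6.2.1 uses the wider term for both agents and the note uses the narrower one, the plain reading leaves ESA outside the note. Sites could read it differently.

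ESA exposure is foreseeable. Exclusion criterion 13a keeps eligible those whose earlier, lower-risk MDS was managed with growth factors.

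CR is the primary efficacy endpoint of an open-label, single-arm study, and the investigators who judge it also decide on ESA. The omission works in one direction: it can add CRs but not remove them. It reaches further endpoints too. Under the EFS rule, a participant without CR within six cycles has an event dated to the start of treatment, so an ESA-supported CR avoids that event. The same participant also enters the duration-of-CR analysis.

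**Working it through.** **1. Does anything in the plan catch an ESA-supported CR?**

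| Place | Transfusion | Myeloid growth factor | ESA |
|---|---|---|---|
| Protocol 6.2.1, permitted support | yes | yes (G-CSF) | yes, named |
| CR note, Table 8-2 and SAP Table 2-2 | barred, 2 weeks | barred, 2 weeks | not mentioned |
| SAP 2.5.1.2, investigator's inputs | listed | listed | not mentioned |
| Protocol 6.2.2, prohibited | no | no | no |
| Estimand, concomitant-medication rule | CR counts | CR counts | CR counts |

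Neither document has an ESA washout or an ESA sensitivity analysis. Hemoglobin alone does not make a CR. The case is a participant who meets every other criterion and needs ESA to reach 10 g/dL.

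**2. The plan's own figures.** Inputs: n = 70; the prior, "Assuming a non-informative prior distribution (Beta(1,1)"; the statistical criterion, "Posterior probability that CR rate is > 39% is at least 97.5%"; and a posterior median of at least 50% (protocol 12.4.2.2).

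With r CRs the posterior is Beta(1 + r, 71 − r):
- r = 35: median 50.0%, P(CR > 39%) = 0.970. Fails.
- r = 36: median 51.4%, P(CR > 39%) = 0.983. Succeeds.

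P(X ≥ 36) for X binomial with n = 70 is 0.0195 at 27/70 (0.0197 at the rounded 38.6%; stated 2.0%) and 0.8005 at 39/70 (stated 80%). These reproduce and are not in dispute.

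**3. Weight of one CR in the planned design.** 1/70 = 1.4 points. At the boundary, reclassifying one CR (36 to 35) reverses the decision.

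**4. Illustration only.** Assume that the 39% benchmark is free of ESA-supported CRs, that the true ESA-free rate here is also 39%, and that ESA support adds d points:

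| d | P(X ≥ 36) |
|---|---|
| 0 | 2.3% |
| 1 | 3.5% |
| 2 | 5.0% |
| 3 | 7.1% |
| 4 | 9.7% |

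Neither document supports any particular d, or the ESA-free benchmark.

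**5. Weight in what will be reported.** SAP 2.5.2.2 keeps only the CR rate by dose level with an exact 95% CI. At the planned 12 in cohort 2, one participant is 1/12 = 8.3 points. For example, 6/12 is 50.0% (21.1% to 78.9%) and 5/12 is 41.7% (15.2% to 72.3%).

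**6. Where would a disallowed CR go?** mCR needs blasts of at most 5% and a fall of at least 50% from baseline. CR needs only the first. A participant going from 8% to 5% falls by 3/8 = 37.5%, so meets the CR marrow criterion but not mCR. Automatic reassignment to mCR would therefore be wrong.

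**The case against.** **The estimand already decides this.** It counts CRs whatever concomitant drug is given, even a prohibited one, so adding ESA to the note would be a preference for a different estimand. This does not settle the matter. The same estimand item covers transfusions, yet the CR definition excludes recently transfused participants. The plan therefore already applies support exclusions inside the definition, before the estimand rule operates. What stands is that changing the note alone would leave the two texts in tension, so the estimand wording needs a clarifying sentence.

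**False success is inflated to as much as 9.7%.** A reader might infer this from the table above. The documents do not support it. They describe the benchmark study only as using IWG-MDS criteria and do not say how it treated ESA. If it also counted ESA-supported hemoglobin, the comparison is like for like, and a stricter rule here would disadvantage this arm.

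**The trial's success decision is at risk.** A reader might infer this too. The SAP (sections 1, 2.5.2.2 and 3) says that the expansion will not be opened and the primary CR analysis will not be performed. The 36/70 rule will not be applied.

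**Stopping ESA produces a relapse.** Not automatically. The hemoglobin criterion needs a fall of at least 1.5 g/dL to below 10 g/dL with no non-MDS explanation, and ESA withdrawal might be such an explanation. SAP 2.5.1.2 also disallows a CR followed by relapse or progression within four weeks, which is a partial safeguard.

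**Purpose, window and visibility.** The purpose of the note is inferred, and neither document gives a basis for a two-week window specific to ESA. Both points stand. Medications are recorded through efficacy follow-up and summarized by ATC class, so ESA use will be visible, but the planned summaries do not link it to CR dates.

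**Conclusion.** The gap is real on the text: an ESA-supported hemoglobin satisfies the CR definition, and no later step removes it. The direction is known (upward only) and the size is not, because ESA use and the benchmark study's ESA rule are both unstated.

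In the planned design a single such CR could have decided the outcome. In the study as it will be reported, the effect is on the descriptive CR rate, the split of CR+mCR between its two parts, duration of CR and EFS. The CR+mCR total would also change for a participant whose blasts fell by less than half. The 8.3-point figure assumes the planned 12 participants in cohort 2. The documents do not support a stated amount of inflation, or a claim that a live success decision is affected. The correction is still worth making because it is cheap and CR remains the headline efficacy result.

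**What to change.** 1. In protocol Table 8-2 and SAP Table 2-2, add ESA to the support exclusion in the CR note, carrying over to PR. Add it to the investigator's inputs in SAP 2.5.1.2. The note's existing two-week window is the simplest choice, and the sponsor should state why it is adequate for ESA. If myeloid growth factor was meant to include ESA, say so.
2. In the estimand, state that the concomitant-medication rule applies to responses that already meet the CR definition, including its support exclusions.
3. When deriving best overall response, compare ESA dates in the concomitant-medication eCRF with each CR date. Class a CR that fails only this condition as mCR if the blast fall of at least 50% is met, and otherwise by the next category for which it qualifies.
4. Report the CR rate with and without ESA-supported cases, so that comparability with the 39% benchmark can be judged and the investigator's assessment stays visible.

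The cost is wording in two tables and two SAP or protocol paragraphs, one programming check on data already collected, and one extra line of output. The reported CR rate may be slightly lower. Clinical use of ESA is unaffected.

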6.2.1.1 Permitted concomitant therapy requiring caution and/or action

Medications to be used with caution during study treatment in this study are listed below. Please also refer to Appendix 2 (see Section 16.2) for detailed guidance.

Strong or moderate CYP3A4 inhibitors and P-gp inhibitors: If, such therapy is necessary, it can be introduced, under the provision that the dose of venetoclax is reduced. Recommendation for venetoclax dose, when given in combination with strong CYP3A inhibitors (e.g., posaconazole, ketoconazole, conivaptan, clarithromycin, indinavir, itraconazole, lopinavir, ritonavir, telaprevir, and voriconazole), moderate CYP3A inhibitors (e.g., erythromycin, ciprofloxacin, diltiazem, dronedarone, fluconazole, and verapamil) or P-gp inhibitors (e.g., amiodarone, azithromycin, captopril, carvedilol, felodipine, quercetin, quinidine, ranolazine, and ticagrelor) are provided in Table 6-2 below.

Table 6-2Management of potential interactions of CYP3A and P-gp inhibitors
with venetoclax

Concomitant drug	Dose Reduction		
Posaconazole	Reduce venetoclax dose to 70 mg		

Novartis	Confidential	Page 48 of 143
Amended Protocol Version 02 (Clean)		Protocol No. CMBG453B12203

Other strong CYP3A inhibitor	Reduce venetoclax dose to 100 mg
Moderate CYP3A inhibitor or P-gp inhibitor	Reduce venetoclax dose to 200 mg

The venetoclax dosage that was used prior to concomitant use with a strong or moderate CYP3A inhibitor or a P-gp inhibitor should be resumed 2 to 3 days after discontinuation of the inhibitor. Participants should be instructed to avoid grapefruit products, Seville oranges, and starfruit during treatment with venetoclax as they contain inhibitors of CYP3A4.

Strong or Moderate CYP3A4 inducers: Concomitant use of venetoclax with strong CYP3A inducers (e.g., carbamazepine, phenytoin, rifampin, St.John's wort) or moderate CYP3A inducers (e.g., bosentan, efavirenz, etravirine, modafinil, nafcillin) should be avoided. Alternative treatments with less CYP3A induction should be considered.

P-gp or BCRP substrates: Co-administration of narrow therapeutic index P-gp, or BCRP substrates (e.g., digoxin, sirolimus) with venetoclax should be avoided.

If a narrow therapeutic index P-gp or BCRP substrate must be used, it should be used with caution. For an orally administered P-gp or BCRP substrate sensitive to inhibition in the gastrointestinal tract (e.g., dabigatran etexilate), its administration should be separated from venetoclax administration as much as possible to minimize a potential interaction.

Anticoagulation therapy is permitted if the participants are already at stable dose of warfarin or stable doses of low molecular weight heparin (LMWH) for > 2 weeks at time of first dose and International Normalized Ratio (INR) should be monitored closely. Participants who develop a new requirement for anticoagulant therapy during the conduct of the study may remain on study after documented discussion with the Novartis medical monitor. However, ongoing anticoagulant therapy should be temporarily discontinued to allow bone marrow sampling according to the institutional guidelines.

Anti-hypertensive therapy is allowed as concomitant medications; however because transient hypotension has occurred during infusions of monoclonal antibodies, consideration should be given to withholding anti-hypertensive medications for 12 hours prior to infusion with sabatolimab.

6.2.2 **Prohibited medication**

During the course of the study, participants must not receive additional investigational drugs, devices, chemotherapy, or any other therapies that may be active against cancer or modulate the immune response.

The use of systemic steroid therapy at immunosuppressive dose (> 10 mg/day of prednisone or equivalent) and other immunosuppressive drugs are not allowed except for the treatment of infusion reaction, immune related adverse events (irAEs), for prophylaxis against imaging contrast dye allergy or in the context of transfusion, for replacement-dose steroids in the setting of adrenal insufficiency or for treatment of transient exacerbation of other underlying diseases such as chronic obstructive pulmonary disease requiring treatment for \leq 3 weeks.

Systemic corticosteroids required for control of infusion reactions or irAEs must be tapered and be at non-immunosuppressive doses ($\leq 10 \text{ mg/day}$ of prednisone or equivalent) before the next sabatolimab administration.

If more than 10 mg/day prednisone is used, sabatolimab should be temporarily interrupted until the participant receives 10 mg/day or less of prednisone.

Topical, inhaled, nasal and ophthalmic steroids are allowed.

The use of live vaccines are not allowed through the duration of the study treatment and 150 days after the last dose of sabatolimab. Inactivated vaccines, subunits recombinant, polysaccharide and conjugate vaccines and toxoid vaccines are allowed.

Vaccination against COVID-19, unless these are live vaccines, is allowed during screening and during the treatment phase but should not be administered on the same day of study treatment administration to avoid potential overlapping adverse events.

In addition, prohibited medication related to azacitidine and venetoclax will apply according to local label.

6.3 **Participant numbering, treatment assignment, randomization**

